1.2 SCHEMA

1.3 SCHEDULE OF ACTIVITIES (SOA)

Procedures	Pre-Index Visit	Index Visit – first eligible visit with primary care	0 to 6 months after Index visit	6 to 12 months after index visit	12 to 18 months after index visit
Select study clinics	Х				
EHR data is exchanged with Wizard web service in the background at the patient's first and subsequent primary care encounters occurring during the study duration. An encounter-based limited data set is collected and stored in a data repository (intervention & control)	х	X	X	x	Х
All eligible patients are randomly assigned a study identification (ID) the first time they are eligible for CDS at a study clinic		х			
Based on the study ID, an eligible patient is then randomly assigned to adherence intervention or control		Х			
After Wizard determines study eligibility and CDS recommendations, it prompts CDS tools to be printed for the intervention-assigned patient and their provider through a Best Practice Advisory (BPA) for rooming staff at each primary care encounter during the study period		X	х	X	X
The eligible intervention-assigned patient has an attempted exposure to Adherence CDS at each primary care encounter during the study period		Х	Х	X	Х
Wizard algorithms are run outside of encounters on all study eligible patients at set intervals (6, 12, and 18 months) for analysis purposes. A limited data set is collected and stored in a data repository (intervention & control patients)			Х	X	X
An eligible intervention-assigned patient is added to a pharmacist outreach intervention registry if study criteria are still met (not at goal and not adherent)			x		
An eligible intervention-assigned patient is assigned to a pharmacist			Х		
Pharmacist calls eligible patient (multiple attempts) for adherence assessment and action plan				X	×
Pharmacist follow-up per action plan				X	Х
Experience and satisfaction surveys sent to a random group of patients (intervention & control)			Х	X	

Procedures	Pre-Index Visit	Index Visit – first eligible visit with primary care	0 to 6 months after Index visit	6 to 12 months after index visit	12 to 18 months after index visit
Safety monitoring per Data Safety Monitoring Board (DSMB) plan (intervention & control)	Х	Х	Х	Х	Х

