9.3 POPULATIONS FOR ANALYSES

The **analysis population** is limited to subjects who meet intervention eligibility requirements at an index visit. We will use data from the Wizard algorithm runs outside the encounter at 6 and 12 months post-index visit to analyze the impact of the intervention on adherence (e-PDC) and clinical outcomes (A1C, BP, statin use). The cost analysis is limited to the subset of these patients who have HealthPartners insurance for at least 11 of 12 months after the index visit.

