The study population will be simulated at the patient level by assigning the known characteristics of the adherence intervention and control groups to synthetic counterparts. Age, sex, race/ethnicity, BMI, systolic BP, cholesterol, smoking status, CV disease history, diabetes status, A1C, and medication use for persons in each study group at the end of the study follow-up period will be entered into the model baseline. Linear, exponential, logarithmic and, if appropriate, polynomial trends, will be fit to the observed intervention differences in medication adherence, CV risk factors, and A1C (identified by H1.1-H.3 and secondary analyses) and used to project future differential trends between the simulated ReachOut adherence intervention and control groups. Incidence of major CV events will be determined using risk equations developed specifically for the model using Framingham Heart Study data.^{130,131} Calculation and reporting of incremental cost-effectiveness ratios (ICERs) will follow the guidelines of the Panel on Cost-Effectiveness in Health and Medicine.¹³² ICERs will be estimated with a 30-year analytic horizon in the primary analysis, and 10- and 20-year horizons will be considered in secondary analyses. Sources of uncertainty will be evaluated using standard sensitivity methods.¹³³

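### The 30-year cost-effectiveness projection extrapolates trends from 12 to 18 months of follow-up, with no bound and no constant or waning base case

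*Combined protocol and SAP*

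**What the plan says.** Section 9.4.3 (Analytic Plan for Long-term Costs and Outcomes) describes the extrapolation. Alongside linear, exponential and logarithmic curves, and only where suitable, "polynomial trends, will be fit to the observed intervention differences" in medication adherence, cardiovascular risk factors and A1C. The fitted curves are "used to project future differential trends between the simulated ReachOut adherence intervention and control groups". On the horizon: "ICERs will be estimated with a 30-year analytic horizon in the primary analysis, and 10- and 20-year horizons will be considered in secondary analyses". The only further safeguard is a general statement that standard sensitivity methods will address uncertainty.

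On the data available, Section 1.3 states: "Wizard algorithms are run outside of encounters on all study eligible patients at set intervals (6, 12, and 18 months) for analysis purposes". Section 9.3 names fewer points for the effect analysis: "Wizard algorithm runs outside the encounter at 6 and 12 months post-index visit". Section 1.1 gives 12 to 18 months of follow-up. Section 4.4 ends the study 12 months after the last index visit, so the 18-month value will be missing for later enrollees.

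Sections 1.3 and 6.1.1 place pharmacist outreach after the 6-month re-evaluation. Until then, intervention patients receive only the enhanced decision support.

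**The concern.** A trend fitted within 18 months says little about year 10 and almost nothing about year 30. A straight line with any non-zero slope eventually becomes too large or changes sign. A rising exponential explodes, and a polynomial is worse. The plan does not limit the projected difference, say for how long a trend is carried, or anchor the base case in a constant or waning effect.

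The staging of the intervention makes a rising slope likely if it works. The 6-month difference reflects decision support alone, while the 12-month difference adds outreach. The increase between them would come from roll-out timing, yet a linear fit would treat it as a permanent annual gain.

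Cost and cost-effectiveness are the secondary endpoints, and Section 3 says these results are meant to inform adoption. If the choice among the listed curves dominates the model input, the ICER reflects that choice more than what the trial observed.

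**Working it through.** Positive values favour the intervention. D is the 12-month planning difference.

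**Inputs from Section 9.2.** SBP: D = 3 mmHg, SD 15.8, correlation 0.5, 80% power, alpha 0.05. A1C: D = 0.3 (9.7% vs 9.4%). Patients with e-PDC of at least 80%: D = 8.7 points (BP drugs), 9.9 (glycemic drugs) and 6.9 (statin), from a 50% control rate.

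**Assumed.** All 6- and 18-month values, because the documents give none; hence a range of patterns.

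**The plan's own figure.** SD of change = 15.8 × √(2(1 − 0.5)) = 15.8. Per arm: 2 × (1.960 + 0.842)² × 15.8² / 3² = 2 × 7.849 × 249.64 / 9 = 435.4, so 436 per arm and 872 in total, as stated.

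**Horizon ratio.** 30 / 1.5 = 20 and 30 / 1 = 30.

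**Straight-line fits.** For equally spaced values at 0.5, 1 and 1.5 years, the least-squares slope per year is (18-month value − 6-month value), and the line passes through the mean at year 1. Year-30 value = mean + 29 × slope.

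| Pattern at 6, 12, 18 months | Mean | Slope | Year 30 | SBP (mmHg) | A1C | e-PDC, BP drugs (points) |
|---|---|---|---|---|---|---|
| 0.8D, D, 1.1D | 0.967D | 0.3D | 9.667D | 29.0 | 2.9 | 84.1 |
| 0.5D, D, D | 0.833D | 0.5D | 15.333D | 46.0 | 4.6 | 133.4 |
| D, D, D | D | 0 | D | 3.0 | 0.3 | 8.7 |
| D, 0.9D, 0.8D | 0.9D | −0.2D | −4.9D | −14.7 | −1.47 | −42.6 |

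With only the two points in Section 9.3 (0.8D, D), the slope is 0.4D and year 30 is D + 29 × 0.4D = 12.6D = 37.8 mmHg.

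**Adherence ceiling, control rate held at 50%.** The gentle rise gives 50 + 84.1 = 134% adherent for BP drugs, 50 + 9.667 × 9.9 = 146% for glycemic drugs and 50 + 9.667 × 6.9 = 117% for statins. For BP drugs the 100% limit is 50 / 8.7 = 5.747D. It is reached at 1 + (5.747 − 0.967) / 0.3 = 16.9 years for the gentle rise and at 1 + (5.747 − 0.833) / 0.5 = 10.8 years for the rise then plateau. Both fall within the 20-year horizon.

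**Sign reversal.** The waning line crosses zero at 1 + 0.9 / 0.2 = 5.5 years, within the 10-year horizon.

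**Other listed forms, SBP at year 30.**
- Logarithmic, gentle rise: slope 0.275D per unit of ln t, mean ln t = −0.096, ln 30 = 3.401. Result: 0.967D + 0.275D × 3.497 = 1.93D = 5.8 mmHg, one fifth of the linear 29.
- Exponential: about 29,500 mmHg for the gentle rise, and about 0.004 mmHg for the waning pattern.
- Quadratic through the three values, gentle rise: D + 29 × 0.3D − 29² × 0.2D = −158.5D = −475.5 mmHg.

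**Precision.** Assume each time point has SE 15.8 × √(2/436) = 1.07 mmHg, with complete data at 18 months. The year-30 linear projection then has SE 1.07 × √(1/3 + 29²/0.5) = 43.9 mmHg if time points are independent, and 31.0 mmHg at correlation 0.5.

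**The case against.** The plan does not commit the base case to a straight line or polynomial. It lists a logarithmic form, which stays plausible here, and admits polynomials only conditionally. A falling exponential decays harmlessly to zero, and a flat effect causes no difficulty under any form. Shorter horizons and sensitivity analyses are planned, and a sensible analyst would reject an absurd curve. All of this stands, and it makes impossible values a possibility, not a certainty. It does not close the gap. The shorter horizons can still include the adherence breach or the sign reversal. The sensitivity statement neither names curve form as a source of uncertainty nor fixes the primary analysis.

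A reader might infer stronger things that the documents do not support:
- *A 90 mmHg SBP or 9-point A1C difference at year 30.* That multiplies 3 and 0.3 by 30, which needs a line from zero at index. Section 9.2 gives these as 12-month differences, not annual rates.
- *At most three data points.* Section 1.3 also stores encounter data, Section 6.1.1 expects 3.5 visits a year, and Section 9.4.3 does not restrict the fit to scheduled runs. Denser data within 18 months would still not support a 30-year extrapolation.
- *Benefit growing after the intervention stops.* Hypothesis 2.2 speaks of a post-intervention simulation, but Section 9.4.3 counts maintenance costs and Section 10.1.4 foresees wider activation. Whether the simulated intervention stops is not stated.
- *An ICER biased in the intervention's favour.* With a waning effect, the plan's linear or exponential fit credits less benefit than a constant difference would.

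**Conclusion.** The concern holds. The primary ICER rests on curves carried 20 to 30 times beyond the observed follow-up, without a bound or a constant or waning base case. For the same 12-month SBP effect of 3 mmHg, straight-line fits give year-30 differences from -14.7 to 46 mmHg, depending on assumed 6- and 18-month values. On one gently rising pattern, linear and logarithmic forms differ fivefold. Both rising patterns put the adherent proportion above 100%.

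These sizes depend on the planning effects, the assumed patterns and a control adherence rate fixed at 50%. They show what the method permits and do not predict the result. The direction of any effect on the ICER is unknown. Only the modelled secondary endpoint is affected. This is a cheap improvement to the plan.

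**What to change.** Amend Section 9.4.3 before outcome data are examined:

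1. In the primary ICER analysis, hold each projected difference constant after follow-up at its last observed estimate, so that it can neither grow in size nor reverse sign. State which time point supplies that estimate, since 18-month data will be incomplete.
2. Present beside it a case in which each difference wanes to zero, with the waning period specified in advance.
3. Keep projected adherence within 0 to 100% in both arms.
4. Report growing trend extrapolations only as labelled scenarios, with the curve form named.

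The cost is a few lines of SAP text and extra model runs. The ICER may become less or more favourable, depending on the observed trend. No data collection and no primary efficacy analysis changes.

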9.4.4 SAFETY ANALYSES

Trends in potential safety concerns for subjects will also be monitored and analyzed as indicated by the Data Safety and Monitoring plan outlined in the safety oversight section below.

9.4.5 BASELINE DESCRIPTIVE STATISTICS

Data extracted will contain patient demographic information including age, sex and race.

Not-applicable

9.4.7 SUB-GROUP ANALYSES

Assessment of heterogeneity of treatment utilization and effects based on pre-specified subgroups of patients will incorporate a factor (e.g. sex) and its interaction with treatment arm in mixed models. A small number of a priori subgroup variables will be tested and include patient sex, age group, race, insurance class (Medicaid, Medicare, commercial), comorbidity count, and pharmacy characteristics.

9.4.8 TABULATION OF INDIVIDUAL PARTICIPANT DATA

Individual participant data will not be listed by measure and time point.

9.4.9 EXPLORATORY ANALYSES

In tertiary/exploratory analysis, we evaluate the impact of the intervention on 10-year CV risk, other objective measures of medication adherence such as PDC, survey assessed patient self-reported adherence, and patient and provider experience and satisfaction as assessed by surveys and interviews. We will also explore differences in intervention use across patient subgroups based on age, gender, race and ethnicity and visit characteristics (such as type of visit, reason for visit, or provider). Treatment arm differences will be assessed using a general or generalized linear mixed-model approach as with the primary analysis, with link functions and error distributions determined by the distribution of each outcome.

Patient and provider experience, satisfaction, facilitators and barriers to implementation will be evaluated using patient and provider surveys and qualitative interviews. Throughout the development and intervention periods, qualitative interviews with key stakeholders which may include clinic and pharmacy leaders, PCPs, clinic staff, pharmacists and patients will be conducted to assess end user experience, enhance design and maximize buy-in. Qualitative interviews may be recorded, transcribed and analyzed ethnographically until thematic saturation is achieved.¹³⁴ Post-implementation, a pharmacist and PCP survey will assess measures of satisfaction, knowledge, use of adherence information, and shared decision-making behaviors.^{135,136} Patient surveys will be conducted with a random sample of about 700 intervention and about 700 control patients. The surveys will be conducted in 2 phases, the first phase occurring within 2 to 4 weeks after index visit and the second phase 2 to 4 weeks after addition to the pharmacist registry to give ample time for the pharmacist outreach to be completed in the intervention subjects >=6 months after the index visit. The second survey sample will include only patients who responded to a question on the first survey consenting to be called again in 6 months for another survey. Surveys will be conducted in a sequential multimode design to simultaneously minimize costs and nonresponse error.^{137,138} Surveys will include questions pertaining to self-reported adherence, barriers to adherence,¹¹¹ shared decision making,¹¹² satisfaction¹¹³, and quality of provider communication.¹³⁹ The patient survey sample size assumes 50% response rates, consistent with those regularly achieved by HP Center for Evaluation and Survey Research, and is large enough to show significance based on results observed with these instruments in previous trials conducted by our research team and others. Existing scales with known psychometric properties will be used for surveys where available. Where no existing scales are available, questions will be developed using best practices to minimize measurement error.¹³⁹

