 Impact of the intervention on overall healthcare costs Predicted long- term health impact and cost- effectiveness of the intervention from the health system (payer) perspective 	 We will measure the cost of delivering the intervention using micro-cost accounting methods and the incremental medical care costs attributable to the intervention, defined from the health system perspective, measured using insurance claims incurred in the median 12-month pre- and post- index date periods by participants with an affiliated HealthPartners insurance plan in each study group. We will use a cardiovascular disease microsimulation model to predict the impact of the intervention on health outcomes and its cost- affective and defined from the 	 If the intervention is found to be effective, the cost of delivering the intervention and its incremental effect on medical care utilization will be important outcomes to informing dissemination and implementation to other systems and settings. A full measurement of the value of the intervention cannot be observed during the study period, but validated microsimulation methods can be used to estimate the full impact of the intervention on preventing or delaying incidence of disease and in averting future medical care costs—both of which will be important to inform the
	effectiveness, defined from the health system perspective, over up to a 30-year prospective time horizon.	translation and adoption of the intervention, if found to be effective.
Tertiary/Exploratory	health system perspective, over up to	translation and adoption of the

	OBJECTIVES		ENDPOINTS	JUSTIFICATION FOR ENDPOINTS
	What are we			
			How are we measuring it?	
	measuring			
1.	The impact of the	1.	We will assess reduction in 10-	The CDS assesses and prioritizes CV
	intervention on		year CV risk measured at each	risks factors according to the
	10-year CV risk		encounter	percentage of 10-year CV risk that
2.	Survey assessed	2.	We will conduct phone surveys	can be reduced if actions are taken
	patient reported		on a random sample of up to	to address the risk factor.
	adherence		1400 eligible patients	
З.	Patient and		approximately 2-4 weeks after an	Provider and patient experience and
	provider		index visit and subsequently ~6	satisfaction information provide end-
	experience and		months later (after a phone	user opinions of the intervention
	satisfaction		outreach has occurred)	which helps to assess impact and

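### The second patient survey is timed from entry to the pharmacist registry, a date that controls and improved intervention patients never have, so its timing and selection may differ by arm

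*Combined protocol and SAP*

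**What the plan says.** Section 9.4.9 describes a two-wave survey of a "random sample of about 700 intervention and about 700 control patients". The first wave falls 2 to 4 weeks after the index visit. For the second, the plan puts "the second phase 2 to 4 weeks after addition to the pharmacist registry", and the stated reason is "to give ample time for the pharmacist outreach to be completed in the intervention subjects >=6 months after the index visit". A separate sentence restricts the second-wave sample to first-wave respondents who agreed to a further call in 6 months. It does not mention the registry.

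The Schedule of Activities (section 1.3) says that "An eligible intervention-assigned patient is added to a pharmacist outreach intervention registry if study criteria are still met", and explains the criteria as being both off goal and nonadherent. Section 6.1.1 describes entry in terms of persistent adherence issues after the 6-month re-evaluation. The same schedule lists the surveys for both arms, in the 0 to 6 and 6 to 12 month columns.

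Section 3 places the survey calls 2 to 4 weeks after an "index visit and subsequently ~6" months later, and adds in brackets that a phone outreach will have taken place by then.

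Section 9.4.9 also says that arm differences in these outcomes will be assessed with mixed models.

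**The concern.** The timing rule depends on an event that only part of one arm can have. Registry entry happens after randomisation, in intervention patients only, and only in those whose problem persisted through 6 months of adherence decision support. Staff who schedule the second survey from registry dates would be following section 9.4.9 as written. They would also have no date for any control or for any intervention patient who improved.

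Two things are at stake. The first wave comes before pharmacist outreach, so the second is the only planned patient survey that can reflect the pharmacist component. The survey also carries the shared decision-making items, and greater patient involvement in medication decisions is one of the trial's stated objectives (sections 1.1 and 4.1). Its standing is not uniform: sections 1.1, 3 and 9.4.9 treat self-reported adherence as tertiary or exploratory, while section 9.4.2 lists it among key secondary variables.

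**Working it through.** **Plan's own figure.** 700 + 700 = 1400, which agrees with section 3 (up to "1400 eligible patients"). No survey effect size, SD or power is given, so the claim that the sample is large enough cannot be recomputed.

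**Three readings of the timing rule.**

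1. Registry entry is required of everyone. No control is surveyed in the second wave, and there is no between-arm comparison.
2. The clause gives timing only, and all consenters are surveyed at about 6 months. Selection is the same in both arms. The date for patients without a registry entry has to be improvised.
3. Registry dates schedule, and so select, the intervention patients, while controls are surveyed at about 6 months. Selection differs by arm.

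**Size under reading 3, with no true effect.** Let f be the share of patients who meet the registry criteria at 6 months (equal in both arms under no effect). Let r be the proportion with good self-reported adherence among them, and r + g the proportion among the rest.

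- Controls, mixed: f × r + (1 − f) × (r + g) = r + (1 − f) × g
- Intervention, registry only: r
- Spurious difference: −(1 − f) × g

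The documents give neither f nor g. I assume f = 0.3, 0.5 and 0.7, and g = 10, 20 and 30 points. The middle value of f is loosely in line with the 50% control adherence at 12 months assumed in section 9.2.

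| f | g = 10 | g = 20 | g = 30 |
|---|---|---|---|
| 0.3 | −7 | −14 | −21 |
| 0.5 | −5 | −10 | −15 |
| 0.7 | −3 | −6 | −9 |

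**Chance of a false finding.** Section 9.4.9 states: "The patient survey sample size assumes 50% response rates". That gives 700 × 0.5 = 350 first-wave responders per arm. If half of them complete the second wave (my assumption), 175 per arm remain. Under reading 3 that means 175 controls against 175 × f intervention patients. With a control proportion of 50% and a two-sided 5% test, the chance of a significant result against the intervention, when there is no effect, is:

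- f = 0.3: 14% to 78%
- f = 0.5: 12% to 64%
- f = 0.7: 7% to 33%

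**Under a common clock.** With 100%, 70% or 50% retained, 350, 245 or 175 per arm are compared. The difference detectable from 50% with 80% power is 10.5, 12.5 or 14.8 points, and the registry selection term is zero.

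**How far apart the two clocks are.** A first survey at 2 to 4 weeks plus about 6 months lands at about 6 months and 2 to 4 weeks after the index visit. Registry entry at the 6-month re-evaluation plus 2 to 4 weeks lands at the same point. For registry patients the two statements nearly agree. The gap concerns patients with no registry date.

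**The case against.** The strongest reply is that the registry clause says when the second wave happens, while the consent sentence says who is in it. That sentence has no registry condition and covers a random sample from both arms. The 6-month wording in section 3, the 6-month consent question and the survey row for both arms in section 1.3 all point to a follow-up at about 6 months for everyone. The biased scenario needs registry entry to act as a condition in one arm and be waived in the other, and no passage says that.

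Most of this stands. A reader might infer that second-wave intervention respondents will be the persistent nonadherers and that the arms are therefore not comparable. The documents do not support that inference, because membership is defined by consent.

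The reply does not supply the missing date, however. Section 3's bracketed condition refers to a phone outreach, which again only registry patients are due. The consent sentence limits the sample to consenters but does not say that every consenter is surveyed whatever their registry status.

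The reply is also right that the size rests on assumed inputs. Leaving the registry criteria is not the same as becoming adherent: under section 1.3 a nonadherent patient who reaches goal also leaves. That would tend to make g smaller than a pure adherent-versus-nonadherent gap.

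**Conclusion.** The point holds as a defect in the timing rule with a conditional bias attached. As written, the second survey has no date for any control or for intervention patients who improved, and sections 9.4.9 and 3 word the clock differently. The documents do not establish that the arms will be incomparable.

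If registry entry decides who is surveyed in the intervention arm only, and registry patients report worse adherence than the rest, the bias runs against the intervention by about 3 to 21 points. This assumes 30% to 70% of patients meet the registry criteria and a self-report gap of 10 to 30 points. If all consenters are surveyed on the same clock, the selection term is zero.

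The reach is limited to second-wave survey outcomes. The first wave and the primary e-PDC, SBP and A1C endpoints are unaffected. The change is still worth making, because a literal reading yields either no control second wave or arm-dependent timing and selection.

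**What to change.** In section 9.4.9, replace the registry anchor with one window for both arms, at a fixed interval after the 6-month Wizard run. Section 1.3 already provides for that run in both arms: "Wizard algorithms are run outside of encounters on all study eligible patients at set intervals (6, 12, and 18 months) for analysis purposes". Keeping the 2 to 4 weeks now written would preserve most of the intended relation to outreach. Align section 3 with the same wording and remove its outreach condition.

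State that all first-survey respondents who agreed to a further call are surveyed regardless of registry status, and that the analysis compares all surveyed patients by randomised arm. Conditioning on first-wave response and consent remains, but the same rule applies in both arms.

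Optionally, flag in both arms who meets the registry criteria at the 6-month run, with no outreach to controls, and report that subset descriptively. Label it a post-randomisation subgroup: intervention patients have had 6 months of adherence decision support by then, so meeting the criteria may itself be affected by treatment. The flag needs a single definition of the criteria, since sections 1.3 and 6.1.1 word them differently.

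The cost is a few revised sentences and, if wanted, one stored flag. The downside is slightly looser timing of the survey relative to each patient's outreach.
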